# 11.3 Statistical Analysis of Secondary Objective 1.2.2 Sleep, Fatigue and Quality of Life

Objective: Using specific measures of sleep quality, excessive daytime sleepiness, daytime activity, fatigue, symptom distress, and quality of life, explore associations of sleep, fatigue and quality of life with other measures of CNS effects, clinical and treatment factors in children and young adults with ependymoma treated with a second course of irradiation.

Stratified by treatment arms (focal vs. craniospinal radiation), descriptive statistics of the longitudinal assessments of sleep, fatigue and quality of life will be described. Specifically, on a yearly basis starting from the pre-treatment time point to year 5 post treatment initiation, quality of life in patients  $\geq 2$  years of age as measured by the PedsQoL brain tumor module will be reported; daytime activity and up to 20 sleep measurements as measured by wrist actigraphy along with sleep diary-patient/parent will be reported. On a more frequent basis (every 3 months for the first 2 years, every 6 month to month 60), sleep complaints in patients  $\geq 8$  years of age as measured by Symptom Distress Scale (SDS) and Epworth Sleepiness Scale will be reported and fatigue in patients  $\geq 2$  years of age as measured by The Peds QL Multidimensional Fatigue scale will be reported, along with PedsQoL brain tumor module. The Acute version of the Multidimensional Fatigue scale and Peds brain tumor module will be administered weekly during radiation therapy.

As an exploratory analysis, each of above mentioned measurements will be compared between two treatment arms by longitudinal data analysis. Generalized Estimating Equation (GEE) will be employed to compare outcome changes over time between two treatment arms by using time and treatment as covariates of the model. The interaction term between treatment arm and time will be added if two arms show different change rate. The other covariates of interest will be selected by Bayesian information criterion (BIC). However, any response with <3 assessments would not be included in the list. To analyze sleep measurements which will be examined annually, the other measurements used in the model will only include their data points measured at the same time as sleep measurements. Multidimensional Fatigue scale and Peds brain tumor module will be measured each week for 4 weeks at the first year. We will analyze them in two ways. First, we will only use the first 4 weeks data to fit the GEE. Second, it will also be fitted in a large time picture but only the first week data of these 4 weeks will be used. In addition, Epworth Sleepiness Scale score will also be dichotomized by 10 and then fitted using GEE with a logistic link.

Similarly, the same modeling approach will be used to explore associations between each of above mentioned outcome and patient characteristics/clinical

St. Jude Children's Research Hospital

IRB NUMBER: Pro00004349
IRB APPROVAL DATE: 02/01/2023

factors that are of interest. The independent effect of resultant significant factors will be explored further in multiple regression models.

Based on the number of tests performed to address this secondary objective, adjustments for multiple comparisons will be made to mitigate over interpreting exploratory findings.

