# 6.7 Sleep, Fatigue and Quality of Life Measures

Actigraphy, will be collected annually as described in Section 2.4. Symptom Distress, Multidimensional Fatigue Standard Version, Epworth Sleepiness Scale and Peds Brain Tumor QoL Generic Version and Peds QoL Generic Version will be administered at baseline and every 3 months for the first 2 years, then every 6 months to month 60. During radiation the Multidimensional Fatigue Acute, Symptom Distress, and Brain Tumor QoL and Peds QoL Acute version (measuring QoL over the last 7 days) will be administered weekly. Parental proxy will be obtained as indicated or if patient is unable to complete the questionnaires.

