## Sleep Measures

Protocol document date: 6/7/2016

Wrist Actigraphy: The Micromini Sleep Watch (Ambulatory Monitoring Inc., Ardsley, NY) is a wristwatch-style device that contains a biaxial piezoelectric sensor and a microprocessor with programmable epoch length. The system's accompanying software will be used to compute the sleep characteristics. Sadeh's algorithm (previously validated against polysomnography in children [81, 86] is the basis of the sleep-wake scoring used in the software program. The actigraph will be applied at baseline for a 5 day sleep assessment and at annual visit.

Sleep Diary-Parent/Patient: The sleep diary will be completed daily by the parent or study participant while wearing the actigraphy.

The Peds QL Multidimensional Fatigue Scale: is an 18-item Likert type scale with three subscales which include general fatigue, sleep/rest fatigue and cognitive fatigue. The patient forms are for three different age groups (5 to 7 year olds, 8 to 12 year olds, and 13 to 18 year olds). There is a parent proxy for each child between the ages of 2-18.

The Symptom Distress Scale (SDS): To be completed by children  $\geq$  7 years of age. The SDS is a 10-item, self-report, Likert type scale developed to measure the patient's degree of discomfort from specific treatment related symptoms (i.e., nausea, sleep disturbances, appetite, etc.). In our previous work using the SDS with adolescents receiving treatment for cancer, the scale achieved coefficient alphas of 0.81 to 0.82. The SDS also was noted to have construct validity, as hypotheses predicting negative relationships with measures of hopefulness, self-esteem, and self-efficacy were all supported. The SDS can be completed in 3 to 5 minutes.

Epworth Sleepiness Scale: To be completed in children  $\geq 7$  years of age. The ESS is an 8-item questionnaire that rates the probability of falling asleep on a scale of increasing probability from 0 to 3 in eight different situations. A total score of 0-9 is normal, while a score of 10 or greater indicates sleep referral. The ESS has been validated in obstructive sleep apnea through the measurement of

Rev 0.1, dated: 9/3/2015

IRB approval date:

St. Jude Children's Research Hospital IRB NUMBER: Pro00004349

excessive daytime sleepiness. We will obtain a parent proxy report for children ages 4-6.

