# Quality of Life

The PedsQL Brain Tumor Module is a 24-item Likert-type scale developed to measure health-related quality of life in children and adolescents who are receiving treatment or survivors' of pediatric brain tumors. The module contains six scales and includes cognitive, pain and hurt, movement and balance, procedural anxiety, nausea, and worry. The research participant's forms are for three different age groups (5 to 7 years, 8 to 12 years, and 13 to 18 years). There is a parent form only for research participants between the ages of 2 and 4 years. There is no patient instrument for children younger than 5 years. The PedsQL Brain Tumor Module forms for the research participant and parents have an internal consistency (Cronbach's alpha coefficients of 0.76-0.87 and 0.78-.92, respectively) with construct validity supported through an analysis of the intercorrelations with the Peds QL and Fatigue Scale [239].

The Pediatric Quality of Life Inventory – PedsQL V.4 is a 23-item Likert-type scale developed to measure health-related quality of life in children and adolescents that takes about 4 to6 minutes to complete. This instrument has parallel forms for patient and parent report, including both acute (QOL within the past 7 days) and longer term (QOL within the past 30 days) forms. The patient forms are for three different age groups (5 to 7 years, 8 to 12 years, and 13 to 18 years). There is a parent form only for age group 2 to 4 years. There is no patient instrument for children younger than 5 years. Subscales on the PedsQL V.4 measure the patients' physical, emotional, social, and school functioning. Both patient and parent forms have been found to be internally consistent (Cronbach's alpha coefficients of 0.91 to 0.92, respectively), with clinical validity (i.e., able to distinguish between known groups of patients on and off-therapy) and beginning construct validity (i.e., hypotheses predicting relationships between certain subscales and other indicators of emotional distress, perceived competency, social support/functioning, and academic competence were supported) [240, 241].

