**Neurocognitive:** Neurocognitive measures are continuous. GEE will be employed to estimate treatment group difference with specific clinical factors and time also included as covariates. For some neurocognitive measures, children and young adults (adolescents) will have different forms. When we pool data together to perform the analysis, we will take these differences into account in the GEE model to control for variations. Neurocognitive measures will also be dichotomized into normal and abnormal groups based on cut-off values (average range vs. outside of the average range for a given test instrument) at specific time points after therapy. GEE with logistic link will be used to investigate the treatment group effect. Frequency and percentage of dichotomized cognitive measures will be calculated.

St. Jude Children's Research Hospital IRB NUMBER: Pro00004349

IRB APPROVAL DATE: 02/01/2023

IRB Approval date:

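### Section 11.3 does not distinguish parent from self-report, or acute from standard forms, in the quality-of-life and fatigue GEE, so a change of respondent or form can pass for a change over time or a difference between arms

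*Combined protocol and SAP*

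**What the plan says.** **Who is analysed.** Section 11.3 takes both scales from age 2. Its text for quality of life runs "years of age as measured by the PedsQoL brain tumor module will be reported", and for fatigue "years of age as measured by The Peds QL Multidimensional Fatigue scale will be reported".

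**Who answers.** For the Brain Tumor module, Section 6.7 (Quality of Life) says: "There is a parent form only for research participants between the ages of 2 and 4 years". Patient forms cover 5 to 7, 8 to 12 and 13 to 18 years. The fatigue scale has the same three patient age bands, and Section 6.7 (Sleep Measures) adds: "There is a parent proxy for each child between the ages of 2-18". The general rule in Section 6.7 is: "Parental proxy will be obtained as indicated or if patient is unable to complete the questionnaires".

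**The model.** In Section 11.3, "each of above mentioned measurements will be compared between two treatment arms by longitudinal data analysis". Time and treatment are the fixed GEE covariates, an interaction is added if the arms change at different rates, and further covariates are chosen by BIC. Neither respondent nor form version is named.

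**Form version.** Sections 6.7 and 11.3 use the acute version during radiotherapy; Section 6.7 uses standard or generic versions at baseline and follow-up. Of the on-treatment scores for these two scales, Section 11.3 says: "it will also be fitted in a large time picture but only the first week data of these 4 weeks will be used".

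**Contrast within the plan.** For cognitive tests whose form depends on age, Section 11.2 promises: "we will take these differences into account in the GEE model to control for variations". Section 11.3 has no such sentence.

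**Age and arm.** In Section 4.3 the focal stratum opens above 12 months of age. All strata that may receive craniospinal irradiation, including the optional 1q-gain stratum, require more than 36 months.

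**The concern.** A parent's rating of a child and the child's own rating are different measurements, and so are acute and standard versions of a questionnaire. An analysis that starts at age 2, with patient forms starting at 5, contains both respondents unless it is split or adjusted, and Section 11.3 commits to neither. A child who passes the fifth birthday during follow-up, or who becomes unable to answer, then shows a step that the model can only attribute to time, to arm, or to their interaction.

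The focal-versus-craniospinal comparison is exposed because the youngest patients, who must have a parent respondent, can be in only one of the two arms. At stake is the reading of the quality-of-life and fatigue trajectories, and of whether they differ by treatment volume.

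**Working it through.** Section 11.3 gives no sample size, effect size or error rate for this objective, so there is no planned figure to reproduce. The check has four parts.

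**1. Visits at which only a parent form exists.** The Section 6.7 schedule is months 0, 3, 6, 9, 12, 15, 18, 21, 24, 30, 36, 42, 48, 54 and 60, which is 15 visits. A visit is proxy-only if age at the visit is 24 to 59 months. Treating age at enrolment as age at month 0:

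| Age at enrolment (months) | Proxy-only visits | Self-report possible |
|---|---|---|
| 24 | 10 of 15 | 5 |
| 36 | 8 of 15 | 7 |
| 48 | 4 of 15 | 11 |
| 60 | 0 of 15 | 15 |

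For example, a child enrolled at 36 months is under 60 months at months 0 to 21, which is 8 visits. A child enrolled before age 5 and followed past that birthday changes respondent once self-report begins, so respondent is tied to time.

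**2. Link with arm.** Children under 3 at enrolment can only be focal. Children aged 3 and 4 at enrolment also start on parent forms but may be in either arm. Suppose enrolment is equally likely in each month of age from 12 to 59. Summing proxy-only visits over those months, 222 come from children enrolled at 12 to 35 months and 108 from those enrolled at 36 to 59 months. The share from focal-only children is 222/(222 + 108) = 67%. If the older band is 2, 3 or 4 times as common per month, it is 222/(222 + 216) = 51%, 222/(222 + 324) = 41% or 222/(222 + 432) = 34%. The documents do not give the age mix.

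**3. Size of the arm bias.** Approximate bias = respondent gap × difference in proxy share. Neither input is in the documents, and the point scale is itself assumed (0 to 100), since Section 6.7 says only that the items are Likert-type.

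| Gap (points) | Share difference 5 pp | 10 pp | 20 pp | 30 pp |
|---|---|---|---|---|
| 5 | 0.25 | 0.5 | 1.0 | 1.5 |
| 10 | 0.5 | 1.0 | 2.0 | 3.0 |

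**4. Effect on slopes.** An illustrative simulation used 45 children per arm, 25 replicates, exchangeable correlation, no true arm or time effect, and parents scoring lower than children. Proxies were forced by age only. With a deliberately young age mix, the proxy share was about 14 to 15% in the focal arm and 6 to 7% in the craniospinal arm. Slopes are in points per year:

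| Gap | Time slope, no respondent term | With term | Arm-by-time slope, no term | With term |
|---|---|---|---|---|
| 5 | +0.44 | +0.04 | −0.24 | −0.05 |
| 10 | +0.78 | −0.01 | −0.35 | +0.05 |

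With ages spread evenly up to 21 years, the false time slopes fell to +0.19 and +0.36, and the arm-by-time slopes (−0.11 and −0.09) were close to the −0.07 seen with no gap at all. The baseline arm contrast is too noisy at 25 replicates to interpret: it was +0.38 and −0.42 in the two settings with no gap.

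**Form version, side by side.** Section 11.3 puts the first-week on-treatment score into the long-run series, and that score is an acute-version score. Section 6.7, the reporting paragraph of Section 11.3 and Appendix III call for weekly questionnaires during radiotherapy. The modelling paragraph of Section 11.3 speaks of four weeks. Table 6.0.3 marks on-treatment QOL at weeks 3 and 6 only. Under the table's schedule, the week-1 score that the model needs would not exist.

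**The case against.** The strongest reply is that pooling of respondents is nowhere stated as a rule. It follows from the form rules plus silence, and BIC selection could admit a respondent or age term. Section 2.4 also commits to examining age against sleep, activity and fatigue outcomes. That is fair, and the point is worded accordingly. But BIC selects on fit, not on control of bias, and a covariate that is never named may not be offered to the selection.

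Second, the analysis is labelled exploratory, arms are not randomised, and multiplicity is to be adjusted. This limits the weight of the point but does not remove it: multiplicity adjustment deals with chance, not with a systematic difference between respondents.

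Third, the scope is narrow. This stands. Actigraphy is objective, and the Symptom Distress and Epworth scales are reported in Section 11.3 from age 8, so the Epworth parent report at ages 4 to 6 does not enter.

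Fourth, very young enrolment may be rare. Enrolment before 36 months requires first irradiation before 36 − 9 = 27 months of age. With the 18-to-26-month time to recurrence given in Section 2.2, it requires irradiation before about 10 to 18 months. This also stands as a limit on the arm effect. It bears less on the time effect, because children enrolled at 3 or 4 years switch respondent too.

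**Conclusion.** The concern holds for the Brain Tumor module and the Multidimensional Fatigue scale. Run as written, the model counts a change of respondent or form version as a change over time, and partly as an arm difference. The arm bias is about 0.25 to 3 points under the assumed gaps and share differences. For the young age mix in the simulation, a share difference of about 8 percentage points gives 0.08 × 5 = 0.4 to 0.08 × 10 = 0.8 points. The primary objective is unaffected.

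Three stronger readings are tempting and are not supported:

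- A reader might infer that proxies are concentrated in focal-only children. That is true only of children under 3 at enrolment, and their share of age-forced proxy visits runs from 34% to 67% across the age mixes tried.
- A reader might infer that proxies mark the sickest patients. The documents say only that a proxy is used as indicated or when the patient cannot complete the form. Disease progression is also an off-study criterion in Section 8.1, which limits switching through tumour-related decline.
- A reader might infer a 7-day against 30-day recall mismatch within these two scales. Section 6.7 gives the 30-day period for the PedsQL V.4, which Section 11.3 does not name. What is documented for these scales is acute against standard versions.

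**What to change.** In Section 11.3, for these two scales:

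1. Include respondent (parent or self) as a forced term in the GEE, not left to BIC.
2. Add a sensitivity analysis restricted to self-report from age 5. It is needed because respondent is entangled with age and with inability to answer, which a single term cannot fully separate.
3. Exclude acute-version scores from the long-run model and use them only in the on-treatment model.
4. Reconcile Section 6.7, Section 11.3, Appendix III and Table 6.0.3 on when questionnaires are given during radiotherapy.

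The cost is a few sentences of plan text, carrying respondent and form version as variables in the analysis dataset, slightly fewer data points in the long-run model, and a little more analysis work. Collecting an additional parent form at every visit is not recommended. The documented forms stop at 18 years while enrolment runs to 21, and the protocol is dated January 2023 with primary completion anticipated in May 2023.

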# 11.2 Statistical Analysis of Secondary Objective 1.2.1 Neurological, Endocrine and Cognitive

Objective: To explore potential associations of clinical and treatment factors with the incidence and severity of neurological, endocrine and cognitive deficits in children and young adults with ependymoma treated with a second course of irradiation.

To assess the side effects of radiation therapy in neurology, ophthalmology, audiology, endocrinology, and cognitive state, the data will be collected in a longitudinal setting. The time schedule for data collection is presented in Table 6.0.1 (Evaluations at baseline and follow-up). Since patients treated by focal or craniospinal radiation will be not at random, to compare the treatment effect, we need to adjust other clinical factors to limit the confound effects in the regression models as discuss below. In addition to the analysis plan below, once we have 15 patients in each stratum (a total of at least 45 patients) followed for 1 year, descriptive statistical analyses and regression analyses as discussed below will be conducted. The results of these interim analyses will be submitted for presentation at an appropriate national scientific meeting, as well as to the CT-SRC. There are not expectations that the findings of these interim analyses would raise concerns for the current trial.

**Neurology:** The neurologic signs and symptoms such as seizures, headache, motor sensation, ataxia, cranial nerve deficits and others will be collected. Neurological data will be obtained from the neurological protocol exam form. Grade 3-5 toxicity data as determined by the NCI CTCAE v 4.0 will be reported. The distribution of ordinal outcomes and percentages will be estimated. Mixedeffects Proportional Odds Regression [300] will be performed to estimate their changes over time, and compare severity in the two treatment arms adjusted by confound factors.

**Ophthalmology:** Vision status of a patient will be dichotomized into None and Impaired, according to clinical meanings, as described in Section 6.3. We will

St. Jude Children's Research Hospital IRB NUMBER: Pro00004349

IRB APPROVAL DATE: 02/01/2023

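### Section 11.3 compares change over time between arms with a default model that has no arm-by-time term, so the arm coefficient can carry a pre-treatment gap or hide a divergence

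*Combined protocol and SAP*

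**What the plan says.** Section 11.3 will use GEE to "compare outcome changes over time between two treatment arms by using time and treatment as covariates of the model". The arm-by-time term is conditional: "The interaction term between treatment arm and time will be added if two arms show different change rate". The section gives no test, threshold or decision rule for what counts as a different rate.

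For adjustment it says: "The other covariates of interest will be selected by Bayesian information criterion (BIC". No covariate is forced in, and nothing is said about how the baseline score enters the model.

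The yearly outcomes are reported "on a yearly basis starting from the pre-treatment time point to year 5 post treatment initiation", so the series includes a value taken before re-irradiation.

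Section 11.2, on a different secondary objective, recognises the allocation problem: "Since patients treated by focal or craniospinal radiation will be not at random", it says, "we need to adjust other clinical factors to limit the confound effects in the regression models". Section 11.3 does not repeat this. Section 4.3 sets treatment by pattern of failure and age. Strata 2 and 3 (metastatic, or combined local and metastatic) receive craniospinal treatment. Stratum 1 (local) receives focal treatment from 12 months of age. Stratum 4 (local failure with 1q gain) has craniospinal treatment as an option. All craniospinal strata require more than 36 months of age at enrolment.

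Section 11.3 also sets its own limits. It opens the comparison with "As an exploratory analysis, each of above mentioned measurements will be compared between two treatment arms by longitudinal data analysis" and promises that "adjustments for multiple comparisons will be made to mitigate over interpreting exploratory findings".

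**The concern.** The quantity that answers the stated question is the arm-by-time contrast. A model with only time and arm gives both arms the same slope by construction. Its arm coefficient is an average difference in level over all visits.

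If children in the two arms already differ before re-irradiation, that difference goes straight into the coefficient. A difference is plausible, since arm depends on failure pattern and age, and section 2.4 itself lists age among the characteristics associated with sleep. Conversely, a real divergence after treatment can be averaged away if the interaction is left out. Whether it is left out depends on an unstated look at the same data.

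The covariate step does not reliably repair this. BIC needs a likelihood, which ordinary GEE does not supply. Selection by fit can also drop a factor that separates the arms. Section 11.4, by contrast, names its adjustment covariates in advance.

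What is at stake is the reading of patient-reported and actigraphy outcomes under the two treatments. Section 6.0 (Research Data) allows exploratory results to be presented and published while the trial is still running.

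**Working it through.** Section 11.3 states no sample size, effect size, SD or power, so there is no figure of the plan to reproduce. The check is of what the model estimates, then of its size under stated assumptions.

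**1. What the arm coefficient is.** The default model is E[Y] = b0 + b1·t + b2·A. Change from visit 0 to t is b1·t in both arms, so the difference in change is fixed at zero. With a b3·A·t term, the difference in change is b3·t. If the true arm difference is d at baseline plus s per year, and everyone is seen at years 0 to 5 (mean 2.5), then b2 in the default model estimates d + 2.5s.

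**2. Baseline gap, identical change (s = 0).** Assumed, not in the documents: 45 patients per arm (90 eligible patients from section 3.3, split equally), total SD 1, within-patient correlation 0.6, unadjusted two-sided 5%, no dropout. Six yearly visits follow section 11.3.
- Variance of a patient's mean over m visits = 0.6 + 0.4/m. For m = 6 this is 0.667.
- SE of the arm difference = sqrt(0.667 × 2/45) = 0.172 SD.
- d = 0.5: 0.5/0.172 − 1.96 = 0.95, so the arm term is significant in about 83% of analyses.
- d = 0.3: 0.3/0.172 − 1.96 = −0.22, so about 41%.
- m = 3: SE = sqrt(0.733 × 2/45) = 0.181, giving about 79% and 38%.

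**3. Check by simulation under other assumptions.** Here 40 focal and 50 craniospinal patients (the 22:28 historical mix of Table 11.0 scaled to 90), correlation 0.5, exchangeable GEE, 400 replicates, six visits, and no difference in change:

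| Baseline gap (SD) | Mean arm coefficient | Arm term significant | Arm-by-time significant when always fitted |
|---|---|---|---|
| 0 | 0.008 | 5.5% | 7.7% |
| 0.3 | 0.299 | 45.5% | 3.5% |
| 0.5 | 0.506 | 87.7% | 5.8% |
| 0.8 | 0.795 | 100% | 7.0% |

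The arm coefficient reproduces the baseline gap. The interaction does not pick it up.

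**4. Masking when the interaction is left out.** With d = +0.5 and s = −0.2 per year, step 1 gives 0.5 − 0.2 × 2.5 = 0. In simulation the arm term averaged 0.004 and rejected in 4.5% of replicates, while arm-by-time averaged −0.201 and rejected in 100%. With d = 0 and s = −0.1, the arm term rejected in 38% and arm-by-time in 80%.

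**5. BIC.** One extra parameter lowers BIC when its 1-df chi-square exceeds ln n. With n = 90 patients, ln 90 = 4.50, an entry threshold of p < 0.034. With n = 90 × 6 = 540 patient-visits, ln 540 = 6.29, or p < 0.012. The plan does not say which n applies, or which quasi-likelihood stands in for the likelihood.

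**6. Which covariates can be forced in.** Metastatic status nearly determines arm. Table 11.0 has 22 local patients treated focally, 7 local patients treated craniospinally, and 16 + 5 = 21 distant or combined patients, all craniospinal. With change as the response and metastatic status in the model, only the local patients inform the arm contrast. The variance factor goes from 1/22 + 1/28 = 0.081 to 1/22 + 1/7 = 0.188, and sqrt(0.188/0.081) = 1.52, so intervals are about 52% wider.

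**The case against.** The strongest reply is that the analysis is labelled exploratory, a multiplicity adjustment is promised, and descriptive statistics by arm start at the pre-treatment visit, so a baseline gap would be visible. The plan also adds the interaction when the arms diverge, and factors found significant are taken into multiple regression models.

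Much of this stands:
- A reader might infer that pre-existing differences will be reported as treatment effects. The documents do not say so. It would take a baseline gap, an interaction left out, and retained covariates that fail to remove the gap. Section 11.3 does not say how the arm coefficient will be interpreted.
- A reader might infer that real divergence is always diluted. That happens only when the trigger misses it. A divergence of −0.2 SD per year would be hard to miss.
- A reader might infer that section 11.2 names age or baseline score as confounders. It names neither, and section 11.3 speaks of covariates of interest.
- A reader might infer that no BIC can exist for GEE. Quasi-likelihood variants exist, and some software prints one. The gap is that none is named.
- The percentages in the working use an unadjusted 5% level and full retention. Progression is an off-study criterion (section 8.1) and historical 3-year PFS is 50% (Table 11.1), so six visits for everyone is optimistic.

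What the reply does not meet is the choice of estimate. Multiplicity adjustment limits chance findings, not bias from a baseline gap. By-arm descriptives can show a gap but do not take it out of the model. An exploratory label does not make an average level difference into a difference in change.

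**Conclusion.** The point holds as a mis-targeted default. Section 11.3 asks about difference in change, fits a model in which that difference is zero, and adds the relevant term only after an unspecified look at the data. Because the series includes the pre-treatment visit and the arms are non-randomised, the default coefficient can carry a baseline gap or conceal a divergence.

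The percentages illustrate the mechanism; they do not predict this trial's results. Baseline gap, correlation, split and retention are all assumed. The qualitative result is the same under both sets of assumptions tried: without arm-by-time, the coefficient follows the baseline gap.

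The BIC point is smaller but real, since the selection rule cannot be applied as written without a further choice. All this concerns an exploratory analysis of a secondary objective. It is worth correcting because the correction is cheap.

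**What to change.** Amend section 11.3 so that:
- Every between-arm model contains arm, time and arm-by-time, and the pre-specified contrast is the arm difference in change from baseline.
- The baseline value is handled explicitly, either as part of the response or as a covariate, but not both.
- Age at re-irradiation and other named clinical factors that overlap between arms are forced in without selection.
- Metastatic status is not forced in. The SAP states that it nearly determines arm, that the comparison cannot separate the two, and that results are non-randomised associations.
- Any remaining selection uses QIC, or a mixed model fitted by maximum likelihood with BIC and a stated n.

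As an optional refinement, limit the arm contrast to patients over 36 months at enrolment, where both treatments occur. This removes only the youngest focal patients and matters mainly for the fatigue and quality-of-life measures, which section 11.3 starts at 2 years; it starts the Symptom Distress and Epworth scales at 8.

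The cost is SAP wording and somewhat wider intervals. No new data are needed.
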